6.9.5 ECG Endpoints

For each ECG endpoint, descriptive statistics of the observed values as well as change from study baseline will be presented by treatment group and overall for each assessment timepoint for the Safety Population. 95% confidence intervals for the change from baseline endpoints will also be presented. Shift tables from study baseline to the end of treatment visit for the overall ECG interpretation (normal, abnormal not clinically significant, or abnormal clinically significant) will be provided for each treatment group in the Safety Population. The number and percentage of patients who had PCS ECG values (based on the criteria in Table 7), will be presented by treatment group. Percentages will be calculated relative to the number of patients with available non-PCS baseline values and at least 1 assessment in the corresponding postbaseline period. The numerator will be the total number of patients with available non-PCS baseline values and at least 1 PCS value in the corresponding postbaseline period.

Table 7. Criteria for Potentially Clinically Significant ECG Results

ECG Parameter (unit)	Higher Limit
QRS duration (msec)	≥ 150
PR interval (msec)	≥ 250
QTc interval (msec)	>480

ECG endpoints will also be presented in a by-patient listing.

6.9.6 Physical Examination

Physical examination will be listed at each visit sorted by subject ID. Summary tables of abnormalities will be provided by visit for each treatment group and overall for the Safety Population.

6.10

EXPLORATORY PHARMACOKINETIC (PK) ANALYSIS

7. CHANGES IN THE CONDUCT OF THE STUDY OR PLANNED ANALYSES

The following changes will be made to the analyses described in the study protocol.

- The primary ANCOVA analyses described in Protocol Section 5.9.2 notes the treatment group and the two stratification factors (atrial fibrillation status and baseline peak VO₂ [$< 60\%$ or $\geq 60\%$]) as categorical variable terms and the baseline CPET value (baseline peak VO₂) as the covariate. Instead, the primary ANCOVA model will include treatment group and atrial fibrillation status as categorical variable terms and the continuous baseline peak VO₂ as a covariate.

█ ██████████
█ ██████████
█ ██████████

- Descriptive statistics for continuous safety laboratory, vital signs and ECG change-from-baseline endpoints will include 95% confidence intervals.

Statistical analyses of the following endpoints, using the same methods as the primary efficacy endpoint, will be performed in addition to those described in the study protocol.

█ ██████████
█ ██████████
█ ██████████
█ ██████████
█ ██████████

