5.1.1 Continuous Endpoints

For continuous endpoints (eg, absolute change from baseline and percent change from baseline), an analysis of covariance (ANCOVA) model will be fitted with treatment group and stratification factors as categorical variable terms and the corresponding baseline efficacy value as a covariate. Least squares means (LSMs) and 95% confidence intervals for each treatment group as well as LSM difference between the 40-mg IW-1973 group and the placebo group will be presented, along with the corresponding confidence intervals and p-values. The cumulative distribution function (CDF) of change from baseline will be plotted by treatment group. To aid in the interpretation of the graphical representation of the CDF across treatments, a two-sample Kolmogorov-Smirnov test will be conducted.

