4. DETERMINATION OF SAMPLE SIZE

The study is not designed to formally test a single statistical hypothesis; however, approximately 184 subjects will provide approximately 90% power to detect a mean difference of 1.3 (mL O₂/kg/min) between the 40 mg praliciguat treatment arm and the placebo treatment arm in change from baseline at Week 12 peak VO₂. This estimate is based on the Evaluable Population (defined in Section 6.1), including patients with permanent or persistent atrial fibrillation at Screening, and using the follow assumptions:

- 5% Type I error for a 2-sided test
- Mean Peak VO₂ change from baseline at Week 12 for Placebo arm is 0.0 (mL O₂/kg/min)
- Mean Peak VO₂ change from baseline at Week 12 for 40 mg praliciguat is 1.3 (mL O₂/kg/min)
- Equal standard deviation for all treatment arms at 2.5 (mL O₂/kg/min) for change from baseline at Week 12
- 10% attrition prior to Week 12 CPET
- 10% of the total number of patients were randomized to either the 10 or 20 mg praliciguat dose groups under Amendment 2 of the protocol (or earlier)
- Reduced treatment effect for praliciguat in subjects with permanent or persistent atrial fibrillation at Screening

Additionally, under similar assumptions, this sample size will also provide 90% power to detect a mean difference of 1.5 (mL O₂/kg/min) on the same endpoint on the well-defined subgroup of a minimum of approximately 148 patients without permanent or persistent atrial fibrillation at Screening.

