6.8.2.2 Main Analytical Approach

Corresponding with the primary efficacy objective of the trial, the primary inference for hypothesis testing is the treatment difference between the placebo group and the 40 mg praliciguat group on the change from baseline in peak VO₂ at Week 12. The primary efficacy analysis will be conducted using the Evaluable Population using an analysis of covariance (ANCOVA) model with treatment group and atrial fibrillation stratification factor as categorical variable terms and baseline peak VO₂ value as a covariate. The null hypothesis of the test will be interpreted as equality between the placebo and 40 mg praliciguat groups, and rejection of the null hypothesis as evidence that the 40 mg praliciguat group has a greater effect on change from baseline in peak VO₂ than the placebo group. Data for patients randomized to 10 mg praliciguat or 20 mg praliciguat under Amendment 2 or earlier will not be included in the analysis.

Least squares means (LSMs) and 95% confidence intervals for each treatment group as well as LSM difference between the 40 mg praliciguat group and the placebo group will be presented, along with the corresponding confidence intervals and p-values.

Distribution assumptions of the models will be evaluated for evident departure from normality and non-constant variances by examining the model residuals. Upon examination of the model residuals, a suitable data transformation may be applied, and if the results of these analyses show consistency with those obtained from the original analyses, only results from the original analysis will be reported.

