6.8.7 Subgroup Analyses

Analysis for change from baseline in peak VO₂, 6MWT, [REDACTED]
will be performed for the each of the following subgroups:

- Gender [Male/Female]
- Baseline atrial-fibrillation strata (yes/no)
- Baseline peak VO₂ (mL O₂/kg/min) strata [$\leq 60\%$, $> 60\%$]
- Baseline NT-pro BNP (pg/mL) [≤ 300 , > 300]
- Baseline LVEF ($\leq 50\%$, $> 50\%$)
- Presence of diabetes versus non-diabetes (diagnosis made by currently treated and/or hemoglobin A1c > 6.5)

Subgroup analyses will be performed only if the total number of subjects in each treatment group within a subgroup category is ≥ 10 . ANCOVA models will be used with change from baseline as the response variable, treatment, visit, subgroup, treatment-by-subgroup interaction, treatment-by-visit interaction and baseline stratification factors as fixed effects, and the respective baseline

value as covariate. Appropriate contrasts will be specified to obtain parameter estimates for each subgroup.

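### The SAP leaves the randomised peak VO2 stratum out of the primary ANCOVA and the MMRM; the cost for peak VO2 is small and conditional, but 6MWT and VE/VCO2 slope may lose all adjustment for peak VO2

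*SAP*

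**What the plan says.** Protocol 3.5.2 and SAP 3.3 stratify randomisation by permanent/persistent AF (yes or no) and by baseline peak VO2 (<60% or ≥60% of age- and sex-adjusted normal). SAP 3.3 gives a block size of 4.

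Protocol 5.1.1 states that the ANCOVA for continuous endpoints "will be fitted with treatment group and stratification factors as categorical variable terms", with the endpoint's own baseline value as covariate. Protocol 5.9.2 repeats this for peak VO2.

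SAP 6.8.2.2 fits "treatment group and atrial fibrillation stratification factor as categorical variable terms" with continuous baseline peak VO2. The MMRM row of SAP Table 4 likewise has AF status and continuous baseline peak VO2 but no peak VO2 stratum. SAP Section 7 declares the ANCOVA change: "Instead, the primary ANCOVA model will include treatment group and atrial fibrillation status as categorical variable terms and the continuous baseline peak" VO2. The visible text gives no reason.

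Elsewhere the SAP keeps both factors. The CMH test in 6.8.5 controls for both, and the subgroup models in 6.8.7 include "treatment-by-visit interaction and baseline stratification factors as fixed effects". SAP 6.8.5 also says that the other change-from-baseline endpoints follow the primary method.

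**The concern.** Protocol 3.2 says that patients are stratified by peak VO2 to limit the impact of imbalance in baseline disease severity, so the sponsor regards the factor as potentially prognostic. If a factor is balanced by design but left out of the model, whatever it predicts beyond the retained covariates stays in the residual. The treatment estimate is then more precise than its reported standard error suggests.

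Continuous baseline peak VO2 remains in the model, so the question is how much the stratum adds to it. The stratum is relative to an age- and sex-specific normal, so it carries some information that the raw value does not.

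No planned analysis estimates the overall treatment effect with the stratum certain to be included. The Table 4 row for other covariates applies only if baseline imbalances appear, and blocking within strata is designed to prevent that for this factor.

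The secondary endpoints could be affected more. If the covariate for 6MWT distance and VE/VCO2 slope is each endpoint's own baseline, as Protocol 5.1.1 has it, then removing the stratum removes peak VO2 from those models altogether.

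**Working it through.** **1. The plan's own figure.** SAP Section 4 gives: "5% Type I error for a 2-sided test"; "approximately 184 subjects will provide approximately 90% power to detect a mean difference of 1.3" mL O2/kg/min; "Equal standard deviation for all treatment arms at 2.5"; "10% attrition prior to Week 12 CPET"; and 10% of patients in the 10 or 20 mg arms, which are not analysed for efficacy.

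- Analysed per arm: 184 × 0.9 × 0.9 / 2 = 74.5.
- SE = 2.5 × √(2/74.5) = 0.4096.
- Power = Φ(1.3/0.4096 − 1.96) = Φ(1.214) = 88.8%, against a stated figure of about 90%.
- Patients without AF: 148 × 0.81 / 2 = 59.9 per arm; power = Φ(1.5/0.4567 − 1.96) = Φ(1.324) = 90.7%, against 90%.

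The stated power therefore reproduces from an unadjusted two-sample formula. It does not depend on the stratum.

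**2. Does raw baseline peak VO2 determine the stratum?** The normals in Protocol inclusion criterion 4 run from 27 to 36 mL/kg/min. The 60% cut therefore runs from 0.6 × 27 = 16.2 to 0.6 × 36 = 21.6. At 18 mL/kg/min, a man aged 50–59 is at 18/36 = 50% of normal and a woman aged 60–69 is at 18/27 = 67%. They have the same covariate value but fall in opposite strata, so the answer is no.

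**3. Effect on the primary standard error.** I simulated stratified randomisation in blocks of 4 within four strata, with 166 randomised (184 × 0.9) and 10% loss, leaving about 149 analysed. Both models contain treatment, AF and continuous baseline peak VO2; one adds the stratum.

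Assumptions not in the documents:
- ages uniform from 45 to 87, with the 50–59 normals used for ages 45–49;
- 60% female;
- percent of normal with mean 57% and SD 12%, kept below 80%;
- AF share 36/184;
- marginal SD of change held at 2.5;
- baseline slope as shown in the table.

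There were 5,000 trials per row for the SE and type I error, and 2,500 for power at a difference of 1.3. The extra stratum effect is its absolute size in mL/kg/min beyond the continuous baseline.

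| Baseline slope | Extra stratum effect | SE with stratum | SE without | Ratio without/with | Power with / without |
|---|---|---|---|---|---|
| 0 | 0 | 0.4106 | 0.4098 | 0.998 | 88.8% / 88.7% |
| −0.15 | 0 | 0.3992 | 0.3984 | 0.998 | 89.8% / 89.8% |
| −0.25 | 0 | 0.3779 | 0.3772 | 0.998 | 92.3% / 92.2% |
| −0.15 | 0.5 | 0.3900 | 0.3903 | 1.001 | 90.9% / 90.5% |
| 0 | 1.0 | 0.4030 | 0.4063 | 1.008 | 89.9% / 89.5% |
| −0.15 | 1.0 | 0.3775 | 0.3810 | 1.009 | 93.4% / 93.0% |
| −0.15 | 1.5 | 0.3588 | 0.3682 | 1.026 | 95.3% / 94.8% |
| 0 | 2.0 | 0.3782 | 0.3944 | 1.043 | 92.0% / 90.6% |

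Type I error was 4.6–5.7% without the stratum and 4.6–5.5% with it (Monte Carlo error about 0.3 points). The correlation between raw peak VO2 and the stratum was 0.71.

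**4. Secondary endpoints.** If peak VO2 is absent and the stratum would explain a share r of the residual variance, the SE is wider by a factor of about 1/√(1 − r). The documents give no r. By assumption: r = 0 gives 1.000, r = 5% gives 1/√0.95 = 1.026, and r = 10% gives 1/√0.90 = 1.054.

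**The case against.** The SAP's choice can be defended. The change is prespecified and declared. Preferring a continuous measure to a dichotomised relative of it is ordinary practice. The normals table has no row for ages 45–49 or for exactly 70, although patients are eligible from 45, so the documents do not fully define the stratum. P-values are nominal, and SAP 5.6 puts the emphasis on estimation. SAP 6.8.7 already fits peak VO2 change with both factors and its own baseline. All of this stands and limits the weight of the point. However, 6.8.7 is a subgroup model and not an estimate of the overall effect, and the CMH test needs the stratum assigned to each patient anyway.

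A reader might draw three stronger conclusions that the documents do not support.

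- *The primary standard error is too wide.* Even the direction depends on how much the stratum predicts beyond continuous baseline, and no figure for that is given. Nor does a squared correlation of about 0.50 (0.71²) mean that half the stratum's information is lost. An exact median split of a normal covariate reaches only 2/π = 0.64.
- *The inference is invalid.* Type I error is not inflated, and any error is conservative.
- *The CMH test shows the plan contradicting itself.* CMH cannot take a continuous covariate, so stratifying is its only way to adjust for peak VO2. The subgroup model has its own use for the term, since the stratum is one of its subgroups.

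**Conclusion.** The point holds as a minor one. One of the two randomisation factors is missing from the primary ANCOVA and the MMRM, the protocol had included it, and the retained covariate does not reproduce it.

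For peak VO2, omitting the stratum changes the SE by −0.2% if it adds nothing and by at most about +1% if it adds up to 1.0 mL/kg/min. At the upper end of that range, 1.009² − 1 is about 2% of the sample, or roughly 3 of 149 patients. The SE is 2–4% wider only at 1.5–2.0, which exceeds the 1.3 treatment difference the trial is sized to detect. Power moves by about 0.5 points or less up to 1.5, and by 1.3 points at 2.0. These figures rest on the assumed age, sex and percent-of-normal distributions above.

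The more practical question is the secondary endpoints. As the visible text reads, 6MWT distance and VE/VCO2 slope may have no adjustment for peak VO2 in any form. This is conditional on their covariate being their own baseline. Parts of SAP 6.8.5 and Section 7 are redacted and could say otherwise.

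**What to change.** In SAP 6.8.2.2 and the MMRM row of Table 4, add the randomised peak VO2 stratum (<60% / ≥60%) as a categorical term beside AF status, and keep continuous baseline peak VO2. In 6.8.5, apply the same two stratification terms to 6MWT distance and VE/VCO2 slope, and name the baseline covariate for each. Delete the corresponding bullet in Section 7.

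The cost is one model term and 1 degree of freedom out of about 145. If the stratum is not prognostic, the SE rises by about 0.2%. The stratum and continuous baseline peak VO2 will be collinear, which blurs their own coefficients but does not affect the treatment estimate.

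If the sponsor prefers the reduced model, Section 7 should give the reason, and Table 4 should include an unconditional sensitivity ANCOVA with the stratum. The secondary-endpoint covariates still need to be stated.

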8. DATA HANDLING CONVENTIONS

8.1 END OF TREATMENT ASSESSMENT

Assessments performed at the end of treatment visit will be included in Week 8 and Week 12 evaluations as follows:

- If a patient has a missing Week 8 assessment, but has a non-missing EOT assessment, then the EOT assessment will be used as the Week 8 assessment if the EOT assessment was conducted on or after study day 50.
- If a patient has a non-missing Week 8 assessment and has a non-missing EOT assessment, then the EOT assessment will be used at the Week 12 assessment if the EOT assessment was performed on or after study day 77.

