3. INVESTIGATIONAL PLAN

3.1 OVERALL STUDY DESIGN AND PLAN

This Phase 2, multicenter, randomized, double-blind, placebo-controlled, parallel-group study will evaluate the safety and efficacy of IW-1973 compared with placebo. The study will enroll approximately 184 adults with established heart failure and limited exercise capacity with EF of at least 40% and who have at least 2 of 4 risk factors for HFpEF (diabetes/prediabetes, hypertension, obesity, advanced age) (see [Eligibility Criteria](#)). Patients will be stratified by atrial fibrillation status and by baseline peak VO₂ (<60% or ≥60% of age- and sex-adjusted normal values with respiratory exchange ratio [RER] ≥1.0 as determined by cardiopulmonary exercise test [CPET]) and randomized in a 1:1 ratio to daily IW-1973 or placebo, as described in Section [3.5.2](#). The number of patients admitted with permanent or persistent atrial fibrillation will be limited to under 20% of target enrollment (≤36 patients).

The study will consist of 3 distinct periods, a Screening Period, a Treatment Period, and a Follow-up Period ([Figure 1](#)).

Figure 1. Study Schematic

Screening Period: The Screening Period will begin with the signature of the ICF at the Screening Visit and may last up to 45 days. At the Screening Visit, patients will undergo screening procedures to determine their initial eligibility. At the Baseline Visit, patients will return to the clinic for additional screening procedures to determine their eligibility, including CPET, vital sign measurements, and blood and urine sample collections, and to receive supplies to take home. The end of the Screening Period will coincide with the beginning of the Treatment Period. The Screening Visit may be combined with the Baseline Visit if the patient is fasted for blood and urine collections. CPET and 6-minute walk test (6MWT) must occur within the 14-day period before Randomization.

Treatment Period: The Treatment Period will begin on Day 1 at Randomization and will end after the End of Treatment Visit on Day 85 (-7/+4 days). At the Day 1 Visit, eligible patients will be stratified as described in Section 3.1 and randomized as described in Section 3.5.2 to receive daily IW-1973 or placebo for approximately 12 weeks. Dosing on Days 1 to 14 (± 3) will be BID (twice daily); dosing on Day 15 (± 3) onward will be QD (once daily).

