3.8.11 CPET

CPET will be performed using a study-specific protocol; details will be provided in a CPET study manual. Each study site will be CPET qualified for the study. Patients must use the same form of exercise (treadmill or bicycle) for all 3 CPETs, and the method of exercise should be recorded in the patient's eCRF. In general, patients will exercise to peak capacity beginning with unloaded exercise and continuing with a symptom-limited incremental ramp to peak VO_2 with $\text{RER} \geq 1$. For the baseline CPET, RER must be ≥ 1 . For Week 8 and End of Treatment CPETs, patients should exercise to maximum effort, ideally to $\text{RER} \geq 1$.

CPET should be performed at the same time of day (± 2 h) and should be timed to occur ≥ 1 hour postdose, when applicable. The CPET will precede the 6MWT when applicable, which will be started ≥ 1 hour after the CPET is completed.

CPET measurements for eligibility and for efficacy analyses will be determined by an independent central CPET Core Lab.

At a minimum, the following measures will be determined:

- Peak VO_2 (mL $\text{O}_2/\text{kg}/\text{min}$)
- RER
- Ventilatory efficiency (VE/V CO_2 slope)
- Peak Power Output at Ventilatory Anaerobic Threshold (watts)

Other parameters of interest may be analyzed.

3.8.12 6-minute Walk Test

The distance, in meters, travelled in 6 minutes will be measured using a study-specific 6MWT protocol ([Appendix 6](#)).

The 6MWTs should be performed at approximately the same time of day (within a 4-hour window) and must be started at least 1 hour after CPET is completed, when applicable.

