5.4 HANDLING OF DROPOUTS OR MISSING DATA

All available data will be included.

For ANCOVA analyses, patients with missing change from baseline values will be excluded. No imputation will be performed for missing observations.

For responder analyses, all patients will be included. Patients with missing postdose data at an assessment timepoint will be treated as non-responders for that assessment timepoint

All safety and tolerability data will be summarized and analyzed when data values are available for a patient. Data handling for missing dates and other key safety data are described in Section 8.

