6. ANALYSIS METHODS

6.1 ANALYSIS POPULATIONS

The following populations will be defined for this study:

- **Screened Population:** All screened patients who have signed the informed consent form for the study and received a patient identification number.
- **ITT Population:** All randomized subjects. Patients in this population will be evaluated according to the treatment group they were assigned to at Randomization. However, all summary tables and efficacy analyses performed on this population will only include the treatment groups (placebo and 40 mg praliciguat) specified in the final amended protocol, unless specified otherwise.
- **Safety Population:** All randomized patients who take at least 1 dose of study drug. The Safety Population will be used for all safety assessments. In the event that a subject receives the wrong treatment, the actual treatment will be used. If a patient received more than 1 treatment, then the patient's data will be summarized according to the treatment they received for the longest duration. All summary tables performed on this population will only include the treatment groups (placebo and PRL 40 mg) included in the final amended protocol, unless otherwise specified.
- **Modified Intent-to-Treat (mITT) Population:** All patients in the ITT Population who take at least 1 dose of study drug and have at least 1 evaluable baseline measurement.
- **Evaluable Population:** All patients in the mITT who complete 8 weeks of dosing (± 3 days) and have at least 1 evaluable postbaseline assessment and did not have a dose reduction. Other criteria, such as major protocol deviations that might have a potential impact on efficacy evaluations (see Section 6.2), may be established and reviewed before database lock and unblinding. The Evaluable Population will be the primary analysis population for the efficacy assessment.
- **PK Population:** All randomized patients who take at least 1 dose of praliciguat and have at least 1 postdose assessment with measurable PK concentration levels.

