6.8.2.4 Sensitivity/Supportive Analysis

Table 4. Sensitivity/Supportive Analyses of Primary Efficacy Endpoint

Endpoint/Method	Description	Summary Method
mITT Population - LOCF	Repeat primary efficacy analysis using the mITT Population. A last-observation-carried-forward (LOCF) approach will be used to impute missing Week 12 assessments of change from baseline in peak VO ₂ . Under the LOCF approach, the patient's previous value during the Treatment Period from Week 8 or earlier postbaseline assessments will be used in case of missing Week 12 assessments. In the case of premature discontinuation from the trial, the patient's last available value during the Treatment Period will be used. If no previous postdose value exists, a change-from-baseline value of "0" will be imputed.	Continuous Summary ANCOVA results for Week 12
Subset of mITT-LOCF	Repeat the mITT LOCF analysis on a subset of the mITT Population, excluding patients who had permanent or persistent atrial fibrillation at baseline	Continuous Summary ANCOVA results for Week 12
Evaluable Population With other covariates	If baseline imbalances are apparent for other parameters, include them in the model to adjust for variability	ANCOVA results for Week 12
Evaluable Population including geographic region	Repeat primary efficacy analysis including geographic region, as defined in Appendix 4 - Table 10, in the ANCOVA model.	Continuous Summary ANCOVA results for Week 12
Evaluable Population - Rank Transform	Performed only if there is evidence of non-normality. Change and baseline values will be ranked based on the normalization method of Blom with ties set to the mean. If the results of the sensitivity analysis show consistency with those obtained from the original analysis, only results from the original analysis will be reported.	
MMRM – Evaluable Population	Perform a mixed-effects model repeated measures (MMRM) analysis with change from baseline in peak VO ₂ as the response variable, treatment, visit, treatment-by-visit interaction, and baseline atrial fibrillation status as fixed effects and baseline peak VO ₂ as the covariate with unstructured as the variance-covariance structure. All available data will be included in the analysis. Please see code in Appendix 5.	Continuous Summary MMRM results

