6.8.3 Secondary Efficacy Endpoints

The following secondary efficacy endpoints will be used to evaluate the effect of praliciguat on exercise and functional capacity.

- Change from baseline in 6MWT distance at Week 12. 6MWT is a simple assessment of everyday functional capacity and provides a global evaluation of the organ/physiologic systems involved in exercise. The distance, in meters, travelled in 6 minutes, measured at approximately the same time of day will define the endpoint.
- Change in ventilatory efficiency as defined by VE/VCO₂ slope (minute ventilation/carbon dioxide production) obtained from CPET at Week 12. These values will be provided by an independent central CPET Core Lab
- CPET Responders, defined as patients who improve by at least 1.5 mL O₂/kg/min in peak VO₂ from baseline to Week 12. Patients who are hospitalized or who die due to heart failure during the study treatment period or who are missing Week 12 postdose values will be considered non-responders.

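### SAP 8.1 relabels a completer's Week 12 exercise test as Week 8 when the Week 8 test is missing, which removes an observed primary-endpoint value

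*SAP*

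**What the plan says.** SAP 8.1 has two rules for assessments made at the EOT visit.

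- **Week 8 missing, EOT present:** "the EOT assessment will be used as the Week 8 assessment if the EOT assessment was conducted on or after study day 50". No latest day is given.
- **Week 8 present, EOT present:** the rule opens "If a patient has a non-missing Week 8 assessment and has a non-missing EOT assessment" and then gives the Week 12 label to an EOT assessment on or after Day 77.

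No rule gives the Week 12 label to an EOT assessment when Week 8 is missing.

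The other relevant text:

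- Protocol 3.1: "The Treatment Period will begin on Day 1 at Randomization and will end after the End of Treatment Visit on Day 85", with a window of -7/+4 days. The schedules in both documents treat Week 12 and EOT as one visit.
- Protocol 3.8.11 names two postbaseline CPETs: "For Week 8 and End of Treatment CPETs, patients should exercise to maximum effort".
- SAP 6.1 admits patients to the Evaluable Population if they complete 8 weeks of dosing, "have at least 1 evaluable postbaseline assessment and did not have a dose reduction". A Week 8 CPET is not required.
- SAP 5.4: "For ANCOVA analyses, patients with missing change from baseline values will be excluded". It adds that nothing is imputed.
- SAP 6.8.3, on CPET responders: patients "who are missing Week 12 postdose values will be considered non-responders".
- SAP 6.8.2.4, on the mITT-LOCF analysis: the patient's "previous value during the Treatment Period from Week 8 or earlier postbaseline assessments will be used in case of missing Week 12 assessments".

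**The concern.** The two rules depend on whether Week 8 is present, when they should depend on when the EOT test was done. A completer with a valid CPET inside the Week 12 window loses the Week 12 label only because an earlier test is absent, and no other test can fill the gap.

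The consequences differ by analysis:

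- **Primary ANCOVA and its non-AF subset:** the patient is excluded although the endpoint was measured.
- **CPET responders:** the patient counts as a non-responder even if the measured gain reached 1.5 mL/kg/min.
- **MMRM:** a test from about Day 85 is modelled at Week 8.
- **mITT-LOCF:** the relabelled value is carried forward to Week 12, so it is recovered.

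The sensitivity analysis would thus use an observed Week 12 value that the primary analysis discards. The two could disagree for a clerical reason and be misread as showing sensitivity to missing data.

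**Working it through.** **1. Apply the rules as written.** Completer window: 85 - 7 = 78 to 85 + 4 = 89.

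| Week 8 CPET | EOT day | Label under SAP 8.1 | Week 12 value |
|---|---|---|---|
| present | 77 to 89 | Week 12 | EOT value |
| missing | 50, 76 | Week 8 | none |
| missing | 77, 78, 85, 89 | Week 8 | none |

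The whole completer window lies beyond both cut-points (Days 50 and 77), so every completer without a Week 8 CPET is in the last row.

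**2. Reproduce the planned power.** Inputs from SAP section 4: N = 184, difference 1.3, SD 2.5, two-sided 5%, 10% in the discontinued dose arms, 10% attrition before the Week 12 CPET. Allocation is 1:1.

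- Analysed: 184 × 0.9 × 0.9 = 149.0, or 74.5 per arm.
- Standard error: 2.5 × √(2/74.5) = 0.410. Noncentrality: 1.3/0.410 = 3.17.
- Power: 88.4% by the noncentral t distribution, 88.8% by the normal approximation. Both agree with the stated figure of about 90%.
- Non-AF subgroup: 148 × 0.81 = 119.9, or 59.9 per arm. Power for 1.5 is 90.3% by noncentral t, again consistent with the plan.

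**3. Remove the relabelled patients.** Let *m* be the share of otherwise analysable patients who lack a Week 8 CPET. The documents give no value, so 3%, 5% and 10% are assumptions. Then n per arm = 74.5 × (1 - *m*), and the 95% CI half-width = t(0.975) × 2.5 × √(2/n).

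| *m* | Values lost (149.0 × *m*) | n per arm | Power for 1.3 | CI half-width (mL/kg/min) | Non-AF power for 1.5 |
|---|---|---|---|---|---|
| 0 | 0 | 74.5 | 88.4% | 0.81 | 90.3% |
| 3% | 4 | 72.3 | 87.4% | 0.82 | 89.4% |
| 5% | 7 | 70.8 | 86.7% | 0.83 | 88.8% |
| 10% | 15 | 67.1 | 84.8% | 0.85 | 87.0% |

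This is additional to the planned 10% attrition. That allowance covers patients with no Week 12 CPET, and these patients have one.

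**4. Responder endpoint.** Assume normally distributed changes with the SAP's means (0 and 1.3) and SD 2.5, and the 1.5 threshold.

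- Placebo: P(Z ≥ 1.5/2.5) = P(Z ≥ 0.60) = 27.4%.
- 40 mg: P(Z ≥ (1.5 - 1.3)/2.5) = P(Z ≥ 0.08) = 46.8%.
- Difference: 19.4 points.

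Scoring a share *m* of each arm as non-responders multiplies each rate by (1 - *m*). The difference becomes 18.8, 18.4 or 17.4 points at 3%, 5% or 10%. With unequal shares, 5% on placebo and 10% on active, it is 46.8 × 0.90 - 27.4 × 0.95 = 16.1 points.

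**The case against.** The strongest reply is that nobody would program it this way. The visit is named Week 12/EOT, SAP 5.4 opens by saying all available data are used, and the Day 50 threshold makes most sense for patients who stop early and have their EOT assessments then (Protocol 3.4.2). The rules could also be applied in sequence: once EOT has filled Week 8, Week 8 is no longer missing, so the second rule gives the Week 12 label as well. SAP 8.1 does not forbid using one test twice. Finally, the affected group is narrow, the miss rates are assumed, the p-values are nominal, and the LOCF analysis recovers the value.

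Much of this is fair about intent and size. The rule was probably meant to place early-termination visits, and an upper limit was left out. But SAP 8.1 does not confine itself to early terminators, and its Day 77 cut covers the entire completer window. No other text is said to override it. The sequential reading is unstated and would enter one test at two visits in the MMRM. The literal, sequential and visit-name readings do not produce the same analysis dataset, and that choice should not be left to programming. LOCF is only a sensitivity analysis and does not repair the responder endpoint.

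**Conclusion.** The concern holds on the text as written: SAP 8.1 discards an observed, in-window primary-endpoint value for any completer without a Week 8 CPET. It should be fixed, though the effect is small. At an assumed 3% to 10% miss rate it costs about 1.0 to 3.6 points of power for 1.3 mL/kg/min (88.4 - 87.4 and 88.4 - 84.8) and 0.01 to 0.04 mL/kg/min of CI half-width.

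The rule is the same in both arms, so for the ANCOVA the main effect is lost precision, and no directional bias is claimed. The responder difference does shrink towards zero, by 0.6 to 2.0 points at equal miss rates.

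These sizes rest on the assumed miss rates, the SAP's planning SD and means, normally distributed changes for the responder figures, and an analysed number that makes no allowance for the SAP's exclusion of patients with a dose reduction. The labelling result itself needs none of these assumptions.

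**What to change.** Rewrite SAP 8.1 by study day, keeping its own cut-points:

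- An EOT assessment on or after Day 77 is the Week 12 assessment, whether or not Week 8 is present.
- An EOT assessment on Days 50 to 76 is used as Week 8 only if the scheduled Week 8 assessment is missing.
- One assessment fills one visit only.

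Under this rule a completer's Day 78 to 89 CPET always reaches Week 12, so no observed Week 12 value is lost through labelling. The cost is two lines of SAP text and the matching derivation code, made before unblinding. No new data are needed.
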